2.1.1.8 Cardiovascular risk category

Randomization was stratified by cardiovascular (CV) risk category ("very high" and "high").

The stratification of "high" and "very high" for cardiovascular risk used in the statistical analysis will be programmatically derived based on eCRF data as the last assessment of CV risk prior to first dose of double-blind treatment. The stratification factor recorded at randomization will not be used in the statistical analysis. Strata recorded in the IRT data, and derived strata (from data reported on the eCRF) will be listed and flagged if discrepant.

Whenever "CV risk category" is mentioned throughout the remainder of this document, this refers to the derived CV risk category prior to first dose of double-blind treatment, if not specified otherwise.

2.1.1.9 Last contact date

The last date of contact is defined as the latest date out of assessment dates and event/medication start and end dates. In case of death, autopsy dates will not be considered in determining the last contact date.

2.1.1.10 Reflexive LDL-C

The endpoints involving LDL-C will use a reflexive LDL-C approach. When both calculated and beta-quantified LDL-C are available, calculated LDL-C will be used unless triglycerides are greater than 400 mg/dL or calculated LDL-C is less than 40 mg/dL. When only calculated LDL-C or beta-quantified LDL-C is available but not both, the available one will be used. Only measurements from central lab will be used for the analyses.

2.2 Analysis sets

The **screened set (SCR)** consists of all participants who signed the informed consent. The SCR includes only unique screened participants, i.e., in the case of re-screened participants only the chronologically last screening data is counted.

The **run-in set (RIS)** consists of all participants who enter the run-in phase.

The **randomized set (RAN)** consists of all participants who received a randomization number, regardless of receiving trial medication.

The **full analysis set (FAS)** consists of all randomized participants who received at least one dose of blinded investigational treatment. Following the intent-to-treat principle, participants will be analyzed according to the treatment to which they were assigned at randomization. Efficacy variables will be analyzed based on the FAS.

The **safety set (SAF)** includes all participants who received at least one dose of blinded investigational treatment. Participants will be analyzed according to the blinded investigational treatment received. A participant who receives any amount of double-blind inclisiran throughout the study will be analyzed within the inclisiran treatment group for the safety analyses. Concomitant use of commercially available inclisiran during the study will

not be considered, those are considered as part of the intercurrent events. The SAF will be used for the analyses of safety and tolerability variables.

Additionally, the **AP set** is a subset of the FAS and includes participants with a diagnosis of angina pectoris at baseline, i.e. participant has a recorded medical history of stable angina or unstable angina. and the **PAD set** is a subset of the FAS and includes participants with a diagnosis of peripheral artery disease at baseline, i.e. participant has a recorded medical history of peripheral artery disease.

2.2.1 Subgroup of interest

Subgroup analysis for the following subgroups will be conducted for primary and the secondary endpoints:

- Age groups (18 – <65 years, 65 – < 75 and ≥ 75),
- Sex (male, female),
- CV risk category (very high risk, high risk).

Subgroup analyses will be conducted using the analyses as for primary and secondary endpoints which are included in the testing hierarchy including a subgroup and treatment-by-subgroup factor into the respective statistical analysis model (for negative binomial regression and logistic regression) and subgroup and treatment-by-subgroup, visit-by-subgroup and visit-by-treatment-by-subgroup factor (for MMRM). The estimates for the respective subgroup and corresponding 95% CI will be presented.

Subgroup analyses will only be performed if each subgroup includes more than 10 participants and additionally for binary outcomes if in at least one subgroup 10 events occurred. If there are still convergence issues for the subgroup analyses after considering all steps for in case of non-convergence (see [Section 5.5](#)), age categories may be combined.

2.3 Patient disposition, demographics and other baseline characteristics

2.3.1 Patient disposition

The number of participants screened, randomized and included in the FAS will be presented by treatment group and overall for the SCR.

The reasons for discontinuation prior to randomization (including screening and run-in failures) will be provided for the SCR and RIS. Mis-randomized participants will be considered as screening/run-in failures.

The number and proportion of participants who completed the study, who discontinued the study and the reason for discontinuation from study will be presented in a study disposition table for each treatment group and overall based on the RAN.

The number of participants included in each analysis set will be presented by treatment group using SCR, corresponding percentages will be based on RAN. Participants excluded from analysis sets will be listed with reasons for exclusion.

For each protocol deviation, the number and percentage of participants in RAN for whom the deviation applies will be tabulated by category and deviation term. In addition, a listing of participants with protocol deviations will be provided.

Number and percentage of participants not meeting inclusion/exclusion criteria will be summarized for participants discontinuing prior to randomization.

2.3.2 Demographics and other baseline characteristics

The following participant demographic and baseline characteristics will be summarized descriptively by treatment group for the FAS:

- Age (years)
- Age groups (18 - <25 years, 25 - <45 years, 45 - <65 years, 65 - < 75 and ≥ 75),
- Age groups (18 - <65 years, 65 - < 75 and ≥ 75),
- Sex (male, female, unknown, undifferentiated),
- Country (Germany, Estonia, Latvia, Czech Rep, Spain, France, Poland, Bulgaria)
- Height (cm)
- Body weight (kg)
- BMI (kg/m^2), calculated as weight in kg divided by (height in m)²
- BMI group (< 18.5 kg/m^2 , 18.5 - <25 kg/m^2 , 25-<35 kg/m^2 , ≥ 35 kg/m^2)
- Statin use at baseline visit (% of participants on respective statin),
- Statin dose intensity at baseline visit
- CV risk category (high, very high)
- CV disease history, including but not limited to the following:
 - Myocardial Infarction
 - Unstable Angina
 - Stable Angina
 - Ischemic Stroke
 - Non-Ischemic Stroke
 - Trans ischemic Attack
 - Peripheral Artery Disease
 - Prior PCI
 - Prior stent implantation (Coronary)
 - Prior CABG
 - Primary Dyslipidaemia/ Hyperlipidaemia
 - Familial Hypercholesterolemia
 - Hypertension
 - Heart Failure
 - Atrial Fibrillation
 - Supraventricular Tachycardia

- Diabetes Mellitus
- Diabetic Retinopathy
- Diabetic Nephropathy
- Diabetic Neuropathy
- Alcohol history (Current, Never, Former)
- Smoking and vaping history (Current, Never, Former)
- Fasting Lipid profile
 - Lp(a) (nmol/L)
 - ApoB (μmol/L)
 - LDL-C (mg/dL)
 - HDL-C (mmol/L)
 - non-HDL-C (mmol/L)
 - total cholesterol (mmol/L)
 - triglycerides (mmol/L)
- relevant laboratory tests (Central lab)
 - AST (U/L)
 - ALT (U/L)
 - total bilirubin (μmol/L)
 - CK (U/L)
 - Creatinine Clearance (U/L)
 - eGFR (mL/min/1.73m²),
 - fasting glucose (mmol/L)
 - HbA1c (%)
- vital signs
 - SBP (mmHg),
 - DBP (mmHg),
 - Pulse (bpm)

Baseline values corresponding to laboratory measurements in the lipid panel refer to assessments collected on Day 1 of the study (before the first administration of the blinded investigational treatment).

2.3.3 Medical history

Medical history will be coded with the Medical Dictionary for Regulatory Activities (MedDRA) terminology using the most recent version at the time of database lock.

Relevant medical histories and current medical conditions at baseline will be summarized by system organ class (SOC) and preferred term (PT) and treatment group based on FAS.

2.4 Treatments (investigational treatment, rescue medication, concomitant therapies, compliance)

2.4.1 Investigational treatment / compliance

The duration of the double-blind treatment period will be computed as the time from the first dose of double-blind treatment to the earliest date out of

- last contact date or
- the participant's death or
- the participant's study completion visit (EOS) date.

The on-treatment period duration will be computed as the time from the first first dose of double-blind treatment to the earliest date out of

- the last injection plus exposure attributable time length of 180 days or
- last contact date or
- the participant's death or
- the participant's study completion visit (EOS) date.

This algorithm reflects intended observation period and the planned treatment schedule and the exposure attributable period of the blinded investigational treatment. The duration of the double-blind treatment period and the duration of the on-treatment period will be summarized for the SAF by treatment group descriptively including by duration categories. The duration categories are given by the number of blinded investigational treatment injections (1 to 3).

The participantyears of exposure will be calculated as the sum of duration of on-treatment period for all participants in days divided by 365.25.

The number of participants with dose adjustments (interruptions or permanent discontinuation) and the reasons will be summarized by treatment and all dosing data will be listed.

The number of study injections administered will also be summarized by treatment group.

2.4.2 Open-label study treatment – AxMP (rosuvastatin)

The duration of exposure to open label study treatment (rosuvastatin) will be computed as the time from the first to the last administration of rosuvastatin excluding interruptions (i.e. minus number days where dose interruption is reported). The duration of exposure will be summarized as for the blinded investigational treatment.

The mean daily administered dose of rosuvastatin averaged over time for an individual participant and over investigational treatment arm will be reported for the double-blind treatment period as well as for the on-treatment period. Interruptions are considered with a dose of 0 mg. For every visit, the number of participants by dose of rosuvastatin administered will be presented. Additionally, the reason for reaching their rosuvastatin MTD will be reported by the number of participants for every specific reason by visit and by investigational treatment arm.

The number of participants with dose adjustments (interruptions or permanent discontinuation) and the reasons will be summarized by treatment and all dosing data (dose level and mean dose) will be listed.

2.4.3 Prior and concomitant lipid lowering therapy

Prior medications and significant non-drug therapies are defined as any medication and significant non-drug therapies taken prior to the first dose of double-blind treatment (i.e. started and stopped prior to first dose). Concomitant medications and significant non-drug therapies are defined as those used during the double-blind period (i.e. started or stopped after first dose of double-blind treatment). Medications taken at date of first dose of double-blind treatment are considered as concomitant.

Prior and concomitant lipid lowering therapy will be summarized for the SAF in separate tables and separate from the standard prior and concomitant medication reporting, based on the coding dictionary used. Lipid lowering medications will be presented in alphabetical order, by preferred terms (PT) and grouped by Anatomical Therapeutic Chemical (ATC) class. ATC class refers to the 4th level ATC class. Tables will show the overall number and percent of participants receiving at least one drug of a particular preferred term and at least one drug in a particular ATC class. A participant with multiple medications with the same preferred term is only counted once towards the total of the preferred term. Summaries will be separate for prior medications and concomitant medications. Additional summary is provided for medications taken at Day 1.

The number of participants on any of the four considered LLT medications (ezetimibe, bile acid sequestrants, bempedoic acid, PCSK9 mAb) will be summarized by visit for both investigational treatment arms. Furthermore, the number of participants for whom the protocol-recommended lipid-lowering therapy escalation was not followed will be reported by reason for not following for every visit. Additionally, the number of participants reaching their LDL-C target under LLT escalation will be provided by visit, investigational treatment and rosuvastatin dose. Duration of exposure to LLT medication will be computed and summarized by type of LLT concomitant medication used. Duration of exposure is derived as the total number of days the respective LLT was taken by the participant between first dose of double-blind treatment and last contact date.

2.4.4 Prior, concomitant and post therapies

Prohibited concomitant medications as mentioned in Table 6-3 of the protocol and given during the conduct of the study as well as significant non-drug therapies will be summarized by preferred term.

Prior and concomitant medications (excluding LLTs) will be summarized for the SAF in separate tables based on the coding dictionary used. Medications will be presented in alphabetical order, by preferred terms (PT) and grouped by ATC class. Tables will show the overall number and percent of participants receiving at least one drug of a particular preferred term and at least one drug in a particular ATC class. A participant with multiple medications with the same preferred term is only counted once towards the total of the preferred term.

Summaries will be provided separately for prior medications and concomitant medications. Additional summary will be provided for medications taken at Day 1.

2.5 Analysis supporting primary objective(s)

The primary objective is to demonstrate the superiority of inclisiran on top of ongoing individually optimized LLT compared to placebo on top of ongoing individually optimized LLT on reaching a participant's individual LDL-C target.

2.5.1 Primary endpoint(s)

The primary endpoint for this study is the proportion of participants at Day 90 achieving their individual LDL-C target of less than 55 mg/dL or less than 70 mg/dL, i.e. <55 mg/dL for participants with very high cardiovascular risk and <70 mg/dL for participants with high cardiovascular risk. The participant-individual LDL-C target depends on their cardiovascular risk category at time of the LDL-C measurement and will be evaluated according to the most recent assessment of CV risk as determined by the investigator. Accordingly, the achievement of the participant-individual LDL-C target forms a binary response variable for LDL-C target ("achieved"/"not-achieved") and will be analyzed in the FAS.

2.5.2 Statistical hypothesis, model, and method of analysis

The primary null hypothesis to be rejected is that the odds regarding participants achieving their individually optimized LDL-C target at Day 90 are equal between treatment groups and therefore independent of the injection of inclisiran or placebo.

The primary null hypothesis and the alternative hypothesis tested can be described as:

$$H_{01}: OR := \frac{(p_1(1 - p_1))}{(p_0(1 - p_0))} \leq 1 \text{ vs. } H_A: OR > 1$$

with p_1 and p_0 the proportion of participants achieving their individually optimized LDL-C target in the inclisiran (p_1) or placebo (p_0) group, respectively. If the null hypothesis cannot be rejected no conclusion regarding a superior effect of inclisiran to reach the individual LDL-C target can be drawn.

For the primary analysis, the odds ratio between inclisiran vs. placebo of the participants achieving their individual LDL-C target at Day 90 will be estimated using a logistic regression model. Treatment and CV risk category will be included as factors in the model. The odds ratio, associated 95% confidence interval (CI), and one-sided p-value will be estimated. Details on testing procedure are described in [Section 2.6.2.5](#).

The number and percentage of participants achieving the individual LDL-C target at Day 90 will be presented for each treatment group derived from data as observed after accounting for intercurrent events as described in [Section 2.5.3](#). The odds ratio, associated 95% CI, and one-sided p-value will be derived from multiply imputed data.

2.5.3 Handling of intercurrent events

The general strategy to account for different intercurrent events is summarized in [Table 2-2](#). Additional explanation is given in the following:

1. Discontinuation of investigational treatment:

Follow-up information after permanent discontinuation of investigational treatment, Retrieved Drop Out (RDO) data will be collected at regular study visits and will be included in the analysis, with treatments as assigned at randomization (treatment policy strategy). If no RDO data are collected missing data will be imputed using jump to reference as described in [Section 5.5.3](#).

2. Death:

For participants who die no subsequent LDL-C value can exist, therefore only pre-death data will be considered. For deceased participants the last value measured before death will be included into the analysis (while alive strategy).

3. Use of PCSK9 targeting non-study medication or lipid apheresis:

It could occur that participants are switched to PCSK9 targeting therapy after discontinuation of study medication or receive lipid apheresis. For the primary estimand participants who use PCSK9 targeting non-study medication or lipid apheresis will be considered as not achieving their LDL-C target (composite strategy).

4. COVID-19 pandemic impact on study:

For the primary estimand collected data will be included in the analysis. The treatment groups will be kept as assigned at randomization (treatment policy strategy). All observed data are used for the analyses, missing data are imputed as described in [Section 2.5.4](#).

Table 2-2 Account for different post randomization events for the primary endpoint reaching LDL-C target at day 90

Intercurrent event	Strategy
Permanent discontinuation of investigational treatment	Treatment policy strategy
Death	While alive strategy
Use of PCSK9- targeting non-study medication* or lipid apheresis	Composite strategy
COVID-19 pandemic impact on study	Treatment policy strategy
* evolocumab, alirocumab or commercially available inclisiran	

Change in background medication essentially concerns change in LLT during optimization. A change in background medication is therefore not considered as an intercurrent event because it is part of the treatments compared.

If an assessment at a visit is affected by multiple intercurrent events, strategy for the intercurrent events occurring will be applied considering the following order of decreasing importance: first composite, followed by while alive and treatment policy.

2.5.4 Handling of missing values not related to intercurrent event

Missing values will be imputed by multiple imputation. In a first step the continuous LDL-C level will be imputed by $m = 100$ imputations based on FAS. From the imputed continuous LDL-C level the binary response variable will be derived against the individual LDL-C target and analyzed with the methods described in the related section. Results will be combined according to Rubin's rules on the log scale. The imputation model will impute missing values based on all observed values taking into account strategy applied for the respective intercurrent event. The imputation model will include randomized treatment arm and CV risk category. Details are described in [Section 5.5.3](#).

2.5.5 Sensitivity analyses

As sensitivity analysis the primary analysis will be repeated excluding participants with a protocol deviation (PD) concerning risk category criteria not met. The following PDs are considered for exclusion of participants:

- INCL03: "Cardiovascular risk category criteria not met"
- INCL04a: "Very high risk criteria and LDL-C target met"
- INCL04b: "High risk criteria and LDL-C target met"

2.5.6 Supplementary analyses

2.5.6.1 Relative risk and absolute risk difference

Additionally, the relative risk as well as absolute risk difference and their 95% confidence intervals will be estimated from a Cochran-Mantel-Haenszel test (CMH) stratified for CV risk category. Analysis is based on data as observed after accounting for intercurrent events as described in [Section 2.5.3](#).

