5. Participant on a stable dose of a statin for \geq 30 days. (Please refer to [Table 3-1](#) for statin enrollment targets.). [The investigator must ensure that the participant's individual statin therapy does not meet any contraindication for that participant and does not interfere with the listed eligibility criteria as stated in the local SmPC of the respective statin.].
6. Up to approximately 20% of total participants can be on a stable dose (for \geq 30 days prior to screening) of another LLT on top of statin such as a cholesterol absorbing inhibitor or a bile acid sequestrant, or alternatively, an adenosine triphosphate citrate lyase (ACL) inhibitor, as indicated.
7. Fasting triglyceride < 400 mg/dL.

At Baseline:

8. Fasting triglyceride < 400 mg/dL.
9. Before randomization, despite being treated with the individual MTD of a statin for \geq 30 days and, if applicable, with another LLT on top of statin (stable for \geq 30 days),
 - a. in participants with very high cardiovascular risk: serum LDL-C \geq 55mg/dL.
 - b. in participants with high cardiovascular risk: serum LDL-C \geq 70mg/dL.

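### The relative risk and risk difference for the primary endpoint use as-observed data while the odds ratio uses imputed data, and the SAP leaves unclear whether jump-to-reference participants enter them

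*SAP*

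**What the plan says.** **Odds ratio.** SAP 2.5.2 states: "The odds ratio, associated 95% CI, and one-sided p-value will be derived from multiply imputed data". SAP 2.5.4 adds: "Missing values will be imputed by multiple imputation", with m = 100 in the FAS, the binary response being derived from imputed continuous LDL-C.

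**Percentages, relative risk and risk difference.** The response percentages in SAP 2.5.2 are to be "derived from data as observed after accounting for intercurrent events as described in" Section 2.5.3. SAP 2.5.6.1 puts the stratified Cochran-Mantel-Haenszel relative risk (RR) and risk difference (RD) on the same footing: "Analysis is based on data as observed after accounting for intercurrent events", again with reference to 2.5.3.

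**Intercurrent events (SAP 2.5.3).** A participant who dies contributes the last value before death. A user of PCSK9-targeting non-study medication or lipid apheresis counts as not achieving target. For permanent discontinuation of investigational treatment the section says: "If no RDO data are collected missing data will be imputed using jump to reference as described in" Section 5.5.3.

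**Recorded changes (SAP 4).** For RR and RD, only the move from score statistics to Mantel-Haenszel estimators is listed. Protocol 12.4.2 names RR and RD as supplementary without stating a data basis.

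**Sensitivity analysis (SAP 2.5.5).** The primary analysis is repeated without participants who have deviation INCL03, INCL04a ("Very high risk criteria and LDL-C target met") or INCL04b (its high-risk counterpart). In Protocol 5.1, criteria 3 and 4 are listed under screening. The LDL-C requirement at baseline is criterion 9a/9b, which opens "Before randomization, despite being treated with the individual MTD of a statin". No code numbered 09 is listed in SAP 2.5.5.

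**The concern.** One binary endpoint is summarized by three effect measures under two missing-data rules and possibly two denominators. Target attainment is a common outcome, so many readers, including those using the trial for health technology assessment, will look to RR and RD before the odds ratio. These are the measures that may not follow the estimand's handling of missing values.

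The specification also cannot be programmed without a guess. SAP 2.5.6.1 asks for observed data after applying 2.5.3, yet 2.5.3 itself calls for imputation of discontinuers without retrieved data. One programmer would include them and another would not.

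The second, smaller matter is that the sensitivity analysis evidently means to remove people already at target, but the listed codes appear to reach only the screening visit.

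**Working it through.** **Step 1. Who is counted where.** Reading SAP 2.5.2–2.5.4 against 2.5.6.1:

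| Day-90 situation | Odds ratio | RR / RD |
|---|---|---|
| Observed | observed | observed |
| Died before Day 90 | last value before death | same |
| PCSK9-targeting drug or apheresis | non-achiever | same |
| Inclisiran discontinued, no retrieved data | jump to reference | unclear: 2.5.3 imputes, 2.5.6.1 says observed |
| Missing for any other reason | imputed under missing at random | absent |

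The two bases differ only in the last two rows.

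**Step 2. Inputs.** There is no figure in the plan to reproduce on this point. The attainment rates in the sample size section are blacked out and no missing-data rate is given. The planned 880 per arm comes from SAP 3.1. Everything else here is an assumption:
- p1, p0: attainment among observed inclisiran and placebo participants
- m: share of the arm with a missing Day-90 value of the last two kinds
- f: share of missing inclisiran values that are jump-to-reference cases, imputed at rate p0; the rest are imputed at the arm's own rate

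Using p0 for the jump-to-reference cases is a simplification, because the imputation model in SAP 5.5.3 also conditions on the participant's own earlier values.

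**Step 3. Formula.** The imputed inclisiran rate is q = p1(1 − m·f) + m·f·p0. Imputed RD = q − p0 and imputed RR = q/p0. Hence

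as-observed RD − imputed RD = m·f·(p1 − p0).

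With f = 0 this is zero.

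**Step 4. Results with f = 1 and these cases left out of RR/RD.** At 80% v 40% the as-observed values are RD 0.400 and RR 2.00. At 60% v 30% the as-observed RD is 0.300.

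| m | Participants absent per arm (880·m) | Imputed RD, 80 v 40 | Imputed RR, 80 v 40 | Imputed RD, 60 v 30 |
|---|---|---|---|---|
| 2% | 18 | 0.392 | 1.98 | 0.294 |
| 5% | 44 | 0.380 | 1.95 | 0.285 |
| 10% | 88 | 0.360 | 1.90 | 0.270 |
| 15% | 132 | 0.340 | 1.85 | 0.255 |

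With f = 0.5 the RD gaps are half as large. With f = 0, RD and RR are the same on both bases and only the participants in the second column are lost.

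**Step 5. Effect on one results table.** At 80% v 40%, m = 5% and f = 1, q = 0.78. The imputed odds ratio is (0.78/0.22)/(0.40/0.60) = 5.32. Beside it would stand observed percentages of 80% and 40%, whose odds ratio is (0.80/0.20)/(0.40/0.60) = 6.00. The measures in that table would not agree with one another.

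**Step 6. Sensitivity exclusions.** If deviation codes follow the protocol's criterion numbers, INCL04a/b concerns LDL-C at screening. A participant above target at screening but at target on the Day −10 sample, and randomized in error, would breach criterion 9 and not criterion 4, and would stay in. The documents do not allow a count.

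**The case against.** The case for leaving the plan alone is substantial. The estimand's summary measure is the odds ratio, and its interval and p-value use the imputed data. RR and RD are openly labelled supplementary, their basis is stated, and it matches the displayed counts and percentages. Jump-to-reference cases at Day 90 should be limited: the second injection is due that day, so they are mainly early exits; discontinuers are to be followed; and the Day-90 lipid window runs from day 76 to day 120. All of this stands. It bounds the size of the problem but does not settle the conflict between 2.5.3 and 2.5.6.1.

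Some stronger readings are tempting, and the documents do not support them:

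- *RR and RD drop everyone without a Day-90 value.* They do not. Participants who died and users of PCSK9-targeting drugs or apheresis keep a response under SAP 2.5.3. Jump-to-reference cases are ambiguous, not certainly excluded.
- *RR and RD as specified favour inclisiran.* This holds only if jump-to-reference cases exist and are left out.
- *The sensitivity analysis retains all participants at target at baseline.* It does not. Screening labs double as baseline labs when randomization follows within 7 days (Protocol 8.1). Participants reaching target in run-in are not randomized (3.2). Day −10 results must confirm eligibility (3.3). That leaves people randomized in error.

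On this last matter, it can also be said that SAP 2.5.5 is framed around risk-category deviations, that the INCL04 labels name no visit, and that the protocol summary joins the screening and baseline LDL-C requirements. Nor does being at target at baseline guarantee success at Day 90, since most participants change statin on Day 1. These arguments are fair, and they make this a request for confirmation more than a demonstrated gap.

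**Conclusion.** The inconsistency is real and limited. The odds ratio and the RR/RD for one endpoint rest on different missing-data handling, the SAP contradicts itself on jump-to-reference discontinuers, and its list of changes does not mention the data basis.

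If those discontinuers are omitted, the as-observed RD exceeds the imputed RD by m·f·(p1 − p0). At 80% v 40% with f = 1, the least favourable setting, that is 0.8 points at 2% missing and 6.0 points at 15%. It is zero when missing values are imputed at the arm's own rate. These sizes rest on assumed rates throughout. A reader might infer that the primary result is at risk; it is not, because the confirmatory odds ratio and p-value already use the imputed data.

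The point about SAP 2.5.5 is minor. It rests on inferring visit coverage from code numbers, and the number of participants concerned is unknown.

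**What to change.** 1. In SAP 2.5.6.1, compute the stratified Mantel-Haenszel log RR and RD in each of the 100 existing imputed datasets and pool them by Rubin's rules, transforming the RR back. This also settles the place of the jump-to-reference cases.
2. Show imputed response percentages beside the observed ones. If an as-observed RR and RD are kept, label them as such, give their denominators, and state whether jump-to-reference cases are in.
3. Record the data basis of RR and RD in SAP 4.
4. In SAP 2.5.5, add the deviations from criterion 9a/9b to the exclusions, or confirm that INCL04a/b already covers the baseline visit.

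The cost is a few sentences of SAP text and a few lines of code, since the imputed datasets are needed for the odds ratio anyway. The downside is that RR and RD may come out slightly less favourable.
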